a.1. Overview: Postoperative delirium in older adults is frequent, associated with poor outcomes, and a serious public health problem. Delirium, or an acute confusional state caused by an underlying physiological disturbance,¹ occurs in up to 60% of older patients undergoing major surgery.^{12, 27-30} It is associated with increased mortality, morbidity, cognitive impairment, functional decline, institutionalization following acute care hospitalization, and psychological distress for patients and their families.⁵⁻⁹ Healthcare costs due to all episodes of delirium in the elderly range from \$38 to \$152 billion/year.^{10,11} Older age and impaired cognition prior to surgery are risk factors for postoperative delirium.^{31,32} For many older patients, a postoperative delirium can tip the balance and result in significant reductions in independence and function.³³

a.2. Delirium: A syndrome characterized by a circadian rhythm disturbance. Disrupted sleep-wake cycle occurs in 73-80% of patients with delirium and includes day/night reversal and fragmentation.^{14,16} Motor activity during a delirious episode is also frequently inappropriate in its timing – with daytime somnolence and nighttime hyperactivity, suggesting circadian dysfunction as a possible central mechanism in delirium.^{13,15} The relationship may be bidirectional: sleep deprivation may lead to significant cognitive deficits and may itself cause or worsen delirium.^{13,34,35} Sleep/wake cycle disruption is central to postoperative delirium.

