Dementia Rating	Preoperative	IQCODE from Proxy Interview; CDR based on Testing and Patient Interview
Age/sex/ race/occupational and education	Preoperative	Data Collection from based on Chart Review and Patient/Proxy Interview
Activities of Daily Living (ADL); Instrumental ADL	Preoperative	Katz and Lawton Scales from Patient and Proxy Interviews; Frailty Measure: Modified Fried Criteria
Comorbidities and review of sleep	Preoperative/POD 1 and	Charlson Index from Chart review, ASA score;

patterns;	POD 2	Pittsburgh Sleep Quality Index (baseline); Richards Campbell Sleep Questionnaire (POD 1 and 2)
Blood sample (5 ml)	Preoperatively, POD 1 and 2	Testing for the following inflammatory biomarkers: CRP (all testing will be performed by a research laboratory)
Medication administration (study agents), OR record/hospital course/discharge	Preoperative, PACU, POD 1 and 2	Data Collection based on Chart Review
Adverse events	PACU, POD 1 and 2	SAE + AE Custom-made Data Collection Forms ("Health Questionnaire") from Patient Interview and Records

b. Secondary outcome variables.

Baseline Covariate Measures:

Dementia Assessments: To measure the preoperative cognitive function, 1) patient interview and testing and 2) Informant Questionnaire on Cognitive Decline in the Elderly (IQCODE)⁸³ completed at baseline after interview of a proxy informant, will inform rating of the 6 domains of the Clinical Dementia Rating (CDR)⁸⁴ by the delirium assessor. Evidence for the CDR ratings will be adjudicated by the consensus panel.

Other Baseline Covariates: Demographics, Activities of Daily Living (ADL's),^{85,86} Instrumental ADL's (IADL's),⁸⁷ validated measures of medical comorbidity and severity (Charlson Comorbidity Index,⁸⁸ and ASA physical status classification system⁸⁹), and a validated measure of sleep, Pittsburgh Sleep Quality Index (PSQI)⁹⁰ will be documented preoperatively. The PSQI measures characteristics of nighttime sleep in the prior month: producing a score of 0 – 21 (lower = better sleep) with a cut-off of ≥ 5 indicating poor sleep quality. Richards Campbell Sleep Questionnaire will be collected from the patient on POD 1 and POD 2 to document in-hospital quality of sleep. We will also collect the modified Fried Frailty Criteria at baseline.

c. Statistical plan including sample size justification and interim data analysis.

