Choice of Sample Size; Power Considerations– Why 80 adherent participants? The power to detect a difference in the development of postoperative delirium of an the previously reported effect-size²⁴(30% placebo-treated vs. 3% ramelteon-treated) is greater than 0.90, using the current design of 40 participants in each treatment arm and assuming 30% of the placebo-treated group will develop delirium on POD 1 or 2. This design can detect an 80% reduction in delirium (30% placebo-treated vs. 6% ramelteon-treated) with a power of 0.84. A conservative estimate for power for the continuous outcome (DSRS-98R) measuring delirium severity can be derived by conceptualizing the proposed longitudinal analysis as an independent samples t-test. With alpha of 0.05 and a sample size of 80, and with means in the ramelteon and placebo groups of 5.75 and 11.34, respectively (as reported in Hatta, et al), and SDs of 4.16 and 10.96, we would have 84% power to detect that difference. Power for the planned analysis, which includes 3 post-surgery measurements per participant, and controls for baseline measurement and additional covariates would likely be greater.

Data Analysis-Specific Aim 1:

Analysis 1: Odds of postoperative delirium upon immediate recovery will be modeled via logistic regression with treatment assignment as the covariate of interest, and controlling for baseline MMSE, surgical duration and sleep disorders in all randomized participants in a strict intent to treat model and also in a second analysis among the 80 first-dose adherent participants.⁹¹ Odds of delirium on POD's 1 and 2 will be modeled via a Markov logistic regression model⁹² as a function of treatment assignment, baseline MMSE, and mental status on

the previous day, where two transitions are possible: from normal mental status to delirium and/or coma (abnormal mental states) and the reverse. Correlation of mental status on consecutive days for the same individual will be modeled using generalized estimating equations (GEE).⁹² We will fit models with interactions between treatment group and variables hypothesized to predict treatment response, including baseline MMSE and sleep to determine if treatment response varies as a function of baseline predictors.

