Analysis 2: The continuous DRS-98R severity measure of delirium will be modeled via longitudinal linear regression with correlated observations within participants addressed via the method of GEE with treatment assignment as the covariate of interest and controlling for baseline DRS-98R score, MMSE, surgical duration and sleep disorders.

Data Analysis-Specific Aim 2: Risk of a severe adverse event will be modeled as a function of treatment assignment using logistic regression, as will counts of total adverse events using ordinal logistic regression or Poisson regression as appropriate. Counts of each specific type of AE, as a function of treatment assignment will be scrutinized to determine the power needed to study them in future larger-scale trials.

- d. Early stopping rules. This is a pilot study and will continue until 80 adherent participants are recruited. A Data Safety Monitoring Board will review the data at the end of year one or at recruitment of 40 adherent participants (whichever comes first) to review the unblinded (labelled "A" and "B") data for safety of the intervention. Specifically, for the analyses of rates of delirium in the two groups, we will use a Haybittle-Peto boundary such that the alpha for the interim analysis will be 0.001, and the alpha for the final efficacy analysis will be 0.05.

8. Risks

- a. Medical risks, listing all procedures, their major and minor risks and expected frequency.

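### Age, a named risk factor collected at baseline, is in none of the efficacy models; adding it to the PACU and severity models would recover a small amount of power

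*Combined protocol and SAP*

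**What the plan says.** Section 3.a.1 (Overview) states: "Older age and impaired cognition prior to surgery are risk factors for postoperative delirium". The assessment table in Section 7.a lists the demographic row "Age/sex/ race/occupational and education" as preoperative, and Section 7.b counts demographics among the baseline covariates.

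Section 7.c specifies three efficacy models:

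- **PACU delirium (logistic):** "controlling for baseline MMSE, surgical duration and sleep disorders in all randomized participants".
- **Delirium on POD 1 and 2 (Markov logistic with GEE):** modelled "as a function of treatment assignment, baseline MMSE, and mental status on" the day before.
- **DRS-98R severity (linear GEE):** "controlling for baseline DRS-98R score, MMSE, surgical duration and sleep disorders".

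MMSE is in all three. Age is in none. Surgical duration is in the first and third only. Under Randomization in Section 4.a, allocation balances on two MMSE strata and nothing else. Participants are randomised at the preoperative visit and take the first dose the evening before surgery, so surgical duration is known only after both. The plan gives no reason for leaving age out or for including duration.

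**The concern.** The protocol identifies two patient-level risk factors and adjusts for one. Eligibility starts at 65 with no upper limit, so age can vary widely. With 40 per arm, an omitted prognostic covariate costs some power, and a chance difference in age between arms feeds into the treatment estimate. These are two views of the same loss. Section 7.c itself expects covariate adjustment to add power for the severity outcome, so the choice of covariates matters to the plan's own argument.

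The second strand is surgical duration. A variable that arises after randomisation and the first dose is not a baseline covariate. An analysis described as intent to treat is easier to defend if it does not need the assumption that treatment leaves that variable unchanged.

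**Working it through.** **Inputs from Section 7.c.** The sample is 80, "using the current design of 40 participants in each treatment arm", and the plan is "assuming 30% of the placebo-treated group will develop delirium on POD 1 or 2". Severity means are 5.75 and 11.34, with SDs 4.16 and 10.96. Alpha is 0.05, taken here as two-sided. The 45% PACU rate is from Section 4.a.

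**Assumed, because the documents give no value.** Age odds ratio 1.0 to 2.0 per SD, or partial R² of 0 to 0.20 for severity. MMSE odds ratio 2.0 per SD, sleep 1.5, surgical duration 1.0 or 1.5. A ramelteon PACU rate of 20%.

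**1. The plan's own figures reproduce.**

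- Binary outcome: the plan says "This design can detect an 80% reduction in delirium (30% placebo-treated vs. 6% ramelteon-treated) with a power of 0.84". With the arcsine formula, h = 2·asin(√0.30) − 2·asin(√0.06) = 0.664, and power = Φ(0.664·√20 − 1.96) = 0.844.
- Severity: pooled SD = √((4.16² + 10.96²)/2) = 8.29. The standardised difference is 5.59/8.29 = 0.674. Noncentral t with 78 df gives 0.846, against the stated 84%.

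**2. Severity model with age added.** Residual variance is multiplied by (1 − R²), so equivalent N = 80/(1 − R²).

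| Partial R² of age | Power | Equivalent N |
|---|---|---|
| 0 | 0.846 | 80 |
| 0.02 | 0.853 | 82 |
| 0.05 | 0.863 | 84 |
| 0.10 | 0.881 | 89 |
| 0.20 | 0.915 | 100 |

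**3. Logistic model with age added to the planned terms.** Simulated, n = 80, likelihood-ratio test, independent covariates, 1,500 runs per scenario, Monte Carlo error about 1 point. The 30% vs 6% rows use a single-outcome logistic model, not the Markov model.

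| Rates | Age OR per SD | Duration OR per SD | Planned | Planned + age |
|---|---|---|---|---|
| 45% vs 20% | 1.0 | 1.0 | 0.731 | 0.738 |
| 45% vs 20% | 1.5 | 1.5 | 0.742 | 0.757 |
| 45% vs 20% | 2.0 | 1.0 | 0.740 | 0.778 |
| 45% vs 20% | 2.0 | 1.5 | 0.751 | 0.785 |
| 30% vs 6% | 1.0 | 1.0 | 0.871 | 0.871 |
| 30% vs 6% | 1.5 | 1.5 | 0.873 | 0.877 |
| 30% vs 6% | 2.0 | 1.5 | 0.863 | 0.877 |

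The gain is about 0 to 3.5 points. The largest single result, 3.8, is within simulation error of that. A separate simulation at 45% vs 18%, with an age-MMSE correlation of 0.3, gave gains of about 1 to 2.5 points (0.817 to 0.827, 0.805 to 0.830, 0.833 to 0.841).

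**4. Chance imbalance.** The SE of the difference in mean age, in SD units, is √(2/40) = 0.224. A difference above 0.3 SD in either direction has probability 2·(1 − Φ(0.3/0.224)) ≈ 0.18. At an age odds ratio of 2 per SD, it shifts the treatment odds ratio by a factor of about exp(0.3·ln 2) = 1.23.

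**5. Swapping duration for age instead of adding age.** PACU rates 45% vs 18%, 6,000 runs per scenario:

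| Age OR | Duration OR | With duration | With age instead |
|---|---|---|---|
| 2.0 | 1.5 | 0.795 | 0.816 |
| 1.5 | 1.5 | 0.804 | 0.803 |
| 2.0 | 2.0 | 0.814 | 0.808 |
| 1.5 | 2.0 | 0.820 | 0.788 |

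The direction depends on which covariate is the stronger predictor, and the documents do not say.

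**6. Cost of the extra term.** At a 30% null rate, simulated type I error was 5.7 to 6.1% as planned and 6.1 to 6.7% with age. Expected events at 30% vs 6% are 40·0.30 + 40·0.06 = 14.4. At 45% vs 20% they are 18 + 8 = 26.

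**The case against.** The best defence is that choosing covariates in a pilot is a matter of judgement. MMSE, probably the main predictor, is in every model and is the allocation factor. Baseline DRS-98R is also in the severity model. Any correlation of age with these shrinks the gain, and comorbidity, frailty and dementia ratings are left out too. This stands as far as size goes: the benefit is modest and the plan's choice is not an error. It does not explain why one of the two risk factors that the protocol itself names is left out when the value is already in hand.

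A reader might infer more about surgical duration than the documents support:

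- **That every efficacy model adjusts for it.** The POD 1-2 model does not.
- **That adjusting for it biases the result.** Bias would need ramelteon to alter operating time, and the documents describe no such route.
- **That it wastes precision.** Section 4.a (Choice of Clinical Site) treats long operations as a marker of delirium risk, so duration may be prognostic. Keeping it did not reduce simulated power (0.734 without, 0.751 with, at 45% vs 20%, with age and duration odds ratios of 2.0 and 1.5).
- **That it removes cancelled cases from the intent-to-treat set.** A participant who never has surgery has no PACU outcome either. Section 4.f handles postponed surgery by suspension and a new baseline.

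**Conclusion.** The point holds in a limited form. Age is omitted from all three efficacy models although the protocol names it as a risk factor and collects it. Adding it to the PACU and severity models is a nearly free improvement. In the logistic model the gain is about 0 to 3.5 points of power for an age odds ratio up to 2.0 per SD. For severity it is equivalent to about 4 to 9 of 80 participants at a partial R² of 5 to 10%. All of this rests on an assumed age effect; if age has no effect, the gain is nil. The stated power figures stand.

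The loss comes only from leaving age out. The timing of surgical duration is a point of principle and a reason for transparent reporting. It is evidence neither of bias nor of lost precision.

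**What to change.** Amend Section 7.c before unblinding:

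- Add age in years as a prespecified covariate to the PACU logistic model and the DRS-98R GEE model.
- State that surgical duration is measured after randomisation and the first dose, and report both models with and without it. Prespecify which version is primary.
- Treat age in the POD 1-2 model as optional, since only about 14 participants with delirium are expected at 30% vs 6%.

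The cost is SAP wording, one more model term and at most a slight small-sample rise in type I error. No new data are needed. The logistic treatment odds ratio becomes conditional on age as well, so the benefit appears as power rather than as a smaller standard error of the log odds ratio.

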Choice of study population and outcome measurement time points: Delirium, diagnosed early in recovery from anesthesia, is very common in older adults (45% after recovery from general anesthesia) and predicts delirium in the subsequent postoperative course.^{5,26,27,73} This finding runs contrary to the view that postoperative delirium cannot be diagnosed unless a period of lucidity has occurred following recovery from anesthesia, and that commonly observed confusion and uncooperativeness upon recovery are benign emergence phenomena.⁷⁴ Since **our previous work suggests that the syndrome, regardless of its attribution, predicts delirium in the days following surgery as well as measurable changes in cognitive function,**⁵ we have included two time periods of delirium incidence as our primary outcome: 1) in the PACU after recovery of arousal, hemodynamic, and respiratory function after anesthesia, as measured by Aldrete score \geq 8;⁷⁴ and 2) during POD 1 and 2 independent of status in the PACU. This will allow for the study of preoperative ramelteon on immediate recovery and during the traditionally described delirium incidence in the days following surgery. For participants who discharge early from the hospital (prior to POD 2), delirium assessment will be conducted via telephone. While longer-term follow-up beyond POD 2 is desirable, it is difficult to complete in all patients in this preliminary study due to an institutional trend toward early post-surgery discharge. We plan to recruit patients with significant cognitive impairment at baseline (mild to moderate dementia) by including participants with Mini Mental State Exam (MMSE) scores \geq 15.⁷⁵ Based upon our previous work, distribution of MMSE scores of 24-30, 15-23, and < 15 prior to surgery for this population will be 50-60%, 25-33% and 7-25% respectively. Participants who score below this cut-off are increasingly difficult to test, making delirium diagnosis difficult.

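### The only model for POD 1–2 delirium incidence adjusts for previous-day mental status, measured after dose 1, so it does not estimate the between-arm effect in Hypothesis 1b or the power statement

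*Combined protocol and SAP*

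**What the plan says.** Section 2 (Hypothesis 1) makes two claims against placebo: (a) less delirium in the PACU and (b) less delirium on POD 1 and POD 2. Section 4.a (study population and time points) defines the second primary period as delirium "during POD 1 and 2 independent of status in the PACU". It also states that early delirium "predicts delirium in the subsequent postoperative course".

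The power statement in section 7.c works with cumulative incidence over the two days, "assuming 30% of the placebo-treated group will develop delirium on POD 1 or 2", and concludes: "This design can detect an 80% reduction in delirium (30% placebo-treated vs. 6% ramelteon-treated) with a power of 0.84".

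Analysis 1 in section 7.c gives PACU delirium its own logistic model with no lagged term. POD 1–2 delirium is modelled by a Markov logistic regression "as a function of treatment assignment, baseline MMSE, and mental status on" one day earlier. The changes of state that this model covers are set out as follows: "where two transitions are possible: from normal mental status to delirium and/or coma (abnormal mental states) and the reverse". The same paragraph adds: "Correlation of mental status on consecutive days for the same individual will be modeled using generalized estimating equations". That sentence deals with repeated measures; it does not remove the lag.

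The nearest thing to a plain comparison of arms is in section 7.d, which sets the Haybittle-Peto alphas "for the analyses of rates of delirium in the two groups". It names no model, test or time window.

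**The concern.** Dose 1 is taken the evening before surgery (section 4.a). For POD 2 the lagged covariate is POD 1 status. For POD 1 it is, by strong inference, PACU status, because the table in section 7.a schedules no other delirium assessment between surgery and POD 1. Both come after treatment has started.

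On the plan's own theory ramelteon lowers PACU delirium, and PACU delirium predicts later delirium. The covariate therefore lies on the path from treatment to outcome. Holding it fixed leaves out whatever benefit on POD 1–2 arises from preventing PACU delirium.

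POD 1–2 incidence is the binary outcome behind the sample size. If its only specified model answers another question, Hypothesis 1b has no matching prespecified test or adjusted estimate. The coefficient could not be carried into a phase 3 sample size as an effect on incidence, and the stated power would not be the power of the planned test.

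**Working it through.** **1. The plan's own figure.** Inputs from section 7.c: 30% vs 6%, 40 per arm. Alpha is 0.05 (section 7.d), two-sided by assumption.

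- Standard error = √[(0.30×0.70 + 0.06×0.94)/40] = √(0.2664/40) = 0.0816
- 0.24/0.0816 = 2.941; power = Φ(2.941 − 1.960) = Φ(0.981) = 0.837

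Exact enumeration of the uncorrected chi-square test gives 0.845. The stated 0.84 is thus reproduced by an unadjusted comparison of two proportions. The claim of more than 0.90 for 30% vs 3% also reproduces (0.956 by chi-square).

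**2. Assumptions for the comparison.** The documents give neither the dependence of POD status on PACU status nor the effect on PACU delirium. Placebo PACU delirium is set at 45% (section 4.a, after general anesthesia). Three assumed patterns each give a placebo POD 1–2 incidence of 30–31%:

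| Dependence | POD 1 risk, PACU delirium yes / no | POD 2 risk, POD 1 delirium yes / no |
|---|---|---|
| Strong | 0.52 / 0.05 | 0.55 / 0.05 |
| Moderate | 0.40 / 0.10 | 0.40 / 0.10 |
| Weak | 0.20 / 0.15 | 0.20 / 0.15 |

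**3. Limiting case: PACU delirium falls from 45% to 15% and nothing else changes.** Strong dependence:

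- Placebo: POD 1 risk = 0.45×0.52 + 0.55×0.05 = 0.2615; any POD 1–2 = 1 − 0.7385×0.95 = 0.298
- Ramelteon: POD 1 risk = 0.15×0.52 + 0.85×0.05 = 0.1205; any POD 1–2 = 1 − 0.8795×0.95 = 0.164
- Between-arm odds ratio = (0.1645/0.8355)/(0.2984/0.7016) = 0.46

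The Markov odds ratio is 1.00 by construction. The between-arm value is 0.66 under moderate and 0.94 under weak dependence.

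**4. Same fall in incidence to 6%, different coefficient.** The direct odds ratio on both days was solved so that ramelteon incidence is 6%. For strong dependence with PACU at 15% it is 0.274. Applied to 0.52 and 0.05 it gives 0.229 and 0.0142. POD 1 risk is then 0.15×0.229 + 0.85×0.0142 = 0.046, and any POD 1–2 = 1 − 0.954×0.986 = 0.06.

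| Odds ratio | Strong | Moderate | Weak |
|---|---|---|---|
| Between-arm | 0.15 | 0.14 | 0.15 |
| Markov, PACU to 15% | 0.27 | 0.21 | 0.17 |
| Markov, PACU to 30% | 0.17 | 0.17 | 0.17 |
| Markov, PACU unchanged | 0.12 | 0.14 | 0.16 |

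**5. Power for that fall, 40 per arm, simulated (20,000 trials per scenario).** Each cell gives likelihood-ratio / Wald. The Markov Wald test uses participant-clustered variance, nearer the planned GEE. Separated fits count as non-significant in the Wald figures.

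| Test | Strong | Moderate | Weak |
|---|---|---|---|
| Between-arm | 0.84 / 0.71 | 0.87 / 0.75 | 0.84 / 0.71 |
| Markov, PACU to 15% | 0.51 / 0.40 | 0.70 / 0.58 | 0.81 / 0.68 |
| Markov, PACU to 30% | 0.84 / 0.71 | 0.86 / 0.74 | 0.85 / 0.72 |
| Markov, PACU unchanged | 0.95 / 0.84 | 0.93 / 0.82 | 0.86 / 0.74 |

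With PACU at 15% and strong or moderate dependence, the like-for-like loss is 0.33 and 0.17 (likelihood-ratio) or 0.31 and 0.17 (Wald). Its direction survives mixing the tests, but its size does not: between-arm Wald 0.75 against Markov likelihood-ratio 0.70 is a loss of 0.05.

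**6. Sensitivity (likelihood-ratio).**

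- Both models adjusted for MMSE (assumed one third low, odds ratio 3), PACU to 15%: Markov 0.56, 0.70, 0.84 vs 0.88, 0.87, 0.86.
- Lower PACU rate (assumed 20% falling to 6.7%, since section 8.a also contemplates regional anesthesia; POD 1 risks reset to 0.70/0.10, 0.45/0.14 and 0.22/0.155): Markov 0.75, 0.84, 0.84 vs 0.84, 0.88, 0.84.
- No treatment effect: both models reject in about 5–6% of trials, so type I error is sound.

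**The case against.** The strongest reply is that a large PACU effect would not go unnoticed. PACU delirium is itself a primary period with its own lag-free model. With PACU falling from 45% to 15%, the PACU comparison has power of about 0.86, and the chance that either it or the Markov test rejects is 0.94 to 0.98 (each at 0.05, no multiplicity correction). That stands as a limit on the harm: the trial would probably still signal efficacy. It does not supply a test or estimate for Hypothesis 1b.

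The power loss also depends on unstated quantities. With PACU at 30% or unchanged, like-for-like Markov power is about equal to or above the between-arm figure. This is correct, and it means the size is uncertain; the mismatch of target does not depend on it.

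Powering on a simpler test than the planned one is ordinary practice, and section 7.c does so openly for severity. So reproducing 0.84 is not proof of a defect by itself. The defect is that the planned coefficient measures something other than the powered contrast.

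The wording in section 4.a about independence from PACU status could mean over and above that status. The more natural reading is regardless of it, and on either reading Hypothesis 1b and the power statement still need an unconditional comparison. Section 7.d hints at one without specifying it. Incidence could be recovered by standardising over the fitted PACU and transition models, but the plan does not say so.

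Finally, the two transitions might be meant to have separate treatment coefficients. The text does not settle this, so the simulated powers, which use one common coefficient, are illustrative.

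**Conclusion.** The concern holds. The single model specified for POD 1–2 incidence conditions on a post-dose variable that the plan expects treatment to change, and no lag-free incidence analysis is prespecified. A transition model is a valid tool for onset and persistence; here it does not match the hypothesis or the sample size.

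Confidence in the mismatch is high. Confidence in the size of the power loss is low. Under the stated assumptions the loss ranges from about one third of full power (strong dependence, large PACU effect) to none, and it becomes a gain if PACU status is unchanged. Because doses 2 and 3 follow the PACU assessment, attenuation is more likely than a null coefficient.

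Crude rates by arm can still be tabulated from the panel diagnoses, but no prespecified test accompanies them, and one chosen after unblinding would be post hoc.

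**What to change.** Before unblinding, make the primary POD 1–2 incidence analysis a logistic regression with one record per participant. The outcome is any panel-adjudicated delirium on POD 1 or POD 2, the covariates are randomised arm and baseline MMSE, and there is no lagged state. Keep the Markov model as a secondary description of transitions and state that its coefficient is not the effect on incidence.

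Name the test as well, because events may be sparse. The chance of no events among 40 ramelteon participants is 0.94^40 = 8% at a 6% risk and 0.97^40 = 30% at 3%. Use a likelihood-ratio test, with a Firth-penalised likelihood-ratio or exact test as the named fallback if that arm has no events. At 30% vs 6% the unadjusted likelihood-ratio and Firth tests have power of about 0.84, Fisher's exact test 0.77 and the Wald test about 0.71. This part concerns sparse data and is separate from the lag.

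The cost is analysis-plan wording, with no new data. The downside is some lost power if ramelteon leaves PACU status unchanged: the Markov likelihood-ratio test would then have 0.95, 0.93 and 0.86 against 0.84, 0.87 and 0.84. The cluster-robust Wald version, nearer to what is planned, would not beat the between-arm likelihood-ratio test (0.84, 0.82, 0.74).

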Outcome Measure Specific Aim I – State-of-the-Art Delirium Assessment and Diagnosis: Well-trained research staff will conduct delirium assessments at baseline, to exclude cases of prevalent delirium, and at three later time points (see Figure and Table). This assessment includes: (1) face to face standardized interview of the patient regarding experiences, (2) standardized cognitive testing including the MMSE⁷⁵ and the abbreviated Digit Span,⁸⁰ (3) history from family/friends familiar with the patient’s cognitive baseline, (4) interview of nursing and other medical staff caring for the patient, and (5) review of medical records for evidence of behavioral disturbances and symptoms in previous 24 hours. Information on sleep disturbance is sought from all sources and is a symptom of delirium. Assessors will rate the CAM⁸¹ and the Delirium Rating Scale-Revised ’98 (DRS-R98)⁶² for the prior 24 hours and describe the patient’s behavior and mental state in a written narrative. If a patient is intubated the CAM-ICU⁸² will be administered to determine delirium status. Patients who are comatose will be documented as such. (Preliminary data suggests that this is a rare occurrence <1%) Final adjudication of delirium diagnosis is derived after all data is presented to a panel of expert delirium diagnosticians ([name]).

The primary diagnosis of delirium is based upon meeting all DSM-5 criteria (see appendix), and is determined by consensus of the expert panel - a method currently employed by this group of co-investigators in the STRIDE study.

A second outcome measure will be analyzed using the continuous variable of delirium severity derived from the DRS-98R severity measure.

Outcome Measure Specific Aim II- Adverse Events: All adverse events (AE and SAE) will be collected from the medical record and daily patient assessment using a customized instrument (“Health Questionnaire”) which will systematically probe for known side effects (fatigue, headache and next day somnolence) (see Protection of Human Subjects). Assessment of Outcome and Covariates:

Table: Timing and Content of Patient Assessments

Assessments	Administration	Collection Instrument and Source
Cognition	Preoperative, PACU POD 1 and 2	Mini Mental State Exam Abbreviated Digit Span: Forwards and Backwards
Delirium	Preoperative, PACU, POD 1 and 2	CAM (full) ⁸³ after patient exam + proxy/medical record review or CAM-ICU if intubated; DRS-98R (severity measure)

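### The POD 1-2 primary model conditions on previous-day status and also models consecutive-day correlation by GEE, with no working correlation named; a non-independence choice would in general be inconsistent

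*Combined protocol and SAP*

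**What the plan says.** Protocol section 7.c (Data Analysis-Specific Aim 1, Analysis 1) says of POD 1-2 delirium that its odds "will be modeled via a Markov logistic regression model". The covariates are treatment, baseline MMSE and the patient's mental state one day earlier, and the model allows movement both ways between normal and abnormal states (delirium or coma). It then adds a second device for dependence: "Correlation of mental status on consecutive days for the same individual will be modeled using generalized estimating equations". No working correlation structure is given, and nothing says whether GEE is meant only to supply robust standard errors.

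This model serves half of the primary outcome. Section 4.a (choice of study population and outcome measurement time points) says "we have included two time periods of delirium incidence as our primary outcome": the PACU, and then "during POD 1 and 2 independent of status in the PACU". The sample size rests on the POD 1-2 rate, "using the current design of 40 participants in each treatment arm". No other final model is given for that period.

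The assessment table in section 7.a lists cognition at "Preoperative, PACU POD 1 and 2", and delirium at the same points. If PACU status serves as the previous-day value for POD 1, each patient contributes two rows: PACU to POD 1, and POD 1 to POD 2. The plan does not define the POD 1 lag, so this is an assumption throughout.

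**The concern.** A transition model already carries day-to-day dependence through the lagged outcome. Modelling the correlation of the same days again handles one dependence twice.

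This is more than redundancy, because the lag is a time-varying covariate that equals the earlier response: the POD 2 row contains the POD 1 outcome. A non-diagonal working correlation multiplies the POD 1 residual by that row, and the product does not have mean zero. The usual assurance that GEE is consistent whatever the working correlation therefore does not apply.

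At stake are the treatment and previous-day coefficients in a primary analysis, and an analyst choice that the plan leaves open.

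**Working it through.** **The plan's own figure.** For 30% vs 6%, 40 per arm, two-sided alpha 0.05 (sidedness assumed), unpooled variance: SE = √(0.30×0.70/40 + 0.06×0.94/40) = 0.0816; z = 0.24/0.0816 = 2.94; power = Φ(2.94 − 1.96) = 0.84, as stated. This formula does not use the Markov/GEE model, so it does not bear on the point.

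**The estimating equation.** Let Y0, Y1, Y2 be status in PACU, POD 1 and POD 2. Let x1 = (1, T, MMSE, Y0), x2 = (1, T, MMSE, Y1), μt the fitted probability, st = √(μt(1−μt)) and rt = (Yt−μt)/st. With two rows and working correlation ρ, the off-diagonal part of a patient's contribution is

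−ρ/(1−ρ²) × [x1·s1·r2 + x2·s2·r1].

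If the Markov model is right, the first term has mean zero given the past. The second does not, since x2 and s2 depend on Y1. For binary Y1,

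E[x2·s2·r1 | past] = s1 × [s2(1)·x2(1) − s2(0)·x2(0)],

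where (1) and (0) mean evaluated at Y1 = 1 and 0.

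Illustration with assumed values: intercept −2.2, lag log OR 2, treatment OR 0.5 (log −0.693), average MMSE, no delirium in PACU.

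- Untreated, lag element: s1 = √(0.100×0.900) = 0.300; μ2(1) = expit(−0.2) = 0.450, s2(1) = 0.498; 0.300×0.498 = 0.149.
- Treated, treatment element: s1 = s2(0) = √(0.052×0.948) ≈ 0.223; μ2(1) = expit(−0.893) = 0.290, s2(1) = 0.454; 0.223×(0.454−0.223) ≈ 0.052.

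Neither is zero, so a fixed non-zero ρ biases the solution even when the Markov model is true. In simulated first-order Markov data (400,000 patients), forcing ρ from −0.3 to +0.3 moved the treatment OR from 0.521 to 0.472 (true 0.50) and from 0.225 to 0.173 (true 0.20). The lag OR moved from about 14 to 3.6 (true 7.39). At ρ = 0 the treatment ORs were 0.497 and 0.198.

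**When ρ is estimated.** If the Markov model is right, E[r1·r2] = 0, so the estimate tends to zero (−0.004 to 0.005 at N = 400,000) and the treatment OR is correct (0.498-0.501 for true 0.50). Bias needs both a non-independence structure and dependence that the single lag does not capture.

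**Unequal carry-over.** Lag log OR assumed 0.8 for PACU to POD 1, then 3.0-3.5 for POD 1 to POD 2, with one lag coefficient fitted. Large-sample treatment log OR in six assumed settings:

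| Independence | Exchangeable | Change in size |
|---|---|---|
| −1.57 | −1.66 | 0.09/1.57 = 6% |
| −1.50 | −1.65 | 0.15/1.50 = 10% |
| −1.51 | −1.68 | 0.17/1.51 = 11% |
| −1.53 | −1.71 | 0.18/1.53 = 12% |
| −1.60 | −1.70 | 0.10/1.60 = 6% |
| −1.48 | −1.71 | 0.23/1.48 = 16% |

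In the first and the last two rows the true value was −1.5. In the first row the lag coefficient fell from 1.47 to 0.66 (fitted ρ 0.35); in the third, from 1.41 to 0.75 (ρ 0.27).

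**Patient heterogeneity.** The shift depends on the assumptions:

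- Away from the null: OR 0.502 to 0.476 (log −0.689 to −0.742, 8%) and 0.185 to 0.165 (log −1.687 to −1.802, 7%).
- Toward the null: log OR −0.75 to −0.70 (7%), −0.70 to −0.63 (10%), and OR 0.544 to 0.550 (log −0.609 to −0.598, 2%).
- Negligible: at most 0.003 on the log scale with random-intercept SD 1-2.5 and equal lags.

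In the first example the lag OR went from 7.8 to 3.6.

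**Scale.** At 80 patients the SD of the treatment log OR is about 0.56 (simulated at true OR 0.50). The carry-over shifts of 0.09-0.23 are 0.16-0.41 of that.

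**Null.** With no treatment effect the large-sample OR stayed at 0.99-1.01, and rejection at 80 patients was 4-6% for both fits.

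**The case against.** **The text does not rule out the valid fit.** Working independence with robust standard errors is one way of running GEE, and the plan names no structure. This stands: the plan does not commit to an inconsistent estimator. But independence does not model correlation, and the sentence says that correlation will be modelled. A literal reader would choose exchangeable or AR(1), which coincide with two rows per patient.

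**A reader might infer that the treatment odds ratio is biased whenever the fitted correlation is not zero.** That does not follow. At 80 patients under a correct Markov model, the fitted correlation is seldom zero (SD about 0.16), yet the median OR was 0.481 with exchangeable and 0.479 with independence.

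**A reader might also infer that heterogeneity reliably shrinks the effect and costs power.** The documents give no dependence parameters, and the direction reverses across plausible ones.

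**Unequal carry-over is first a fault in the mean model.** Letting lag and intercept differ by transition gave −1.511 and −1.512 (true −1.5) even with exchangeable correlation. This stands. Independence does not cure that fault: with a single lag it gave −1.48, −1.57 and −1.60. Exchangeable was further from −1.5 in each case (−1.71, −1.66, −1.70).

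**Disagreement between fits on p < 0.05 overstates harm.** It was 9.8% of fitted trials under unequal carry-over, but 5.9% even when the Markov model was right, so much of it is noise.

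**Conclusion.** The point holds in a limited form. The sentence permits, and on its face invites, a non-independence working correlation beside a lagged outcome, which is inconsistent in general. With an estimated correlation, the harm arises only when dependence departs from the fitted first-order form. Such a departure is plausible, since the step out of anaesthesia recovery need not carry over like the step between ward days.

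Under assumed unequal carry-over the treatment log odds ratio is typically about 5-12% larger in size than under working independence; one setting reached 16%. Under heterogeneity the shift is negligible to about 10%, in either direction. Most of these comparisons are with the independence fit, which is itself only an approximation when the model is wrong. The previous-day coefficient is affected far more. The treatment shifts are modest beside sampling error at 40 per arm, and the false-positive rate is not affected.

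All sizes rest on assumed dependence structures and on PACU status being the POD 1 lag. Whether the primary analysis should condition on PACU status, which is measured after the first dose, is a separate question and adds no weight here.

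**What to change.** Replace the GEE sentence in section 7.c with a statement that the transition model is fitted with an independence working correlation and robust, patient-clustered standard errors. The point estimates are then those of ordinary logistic regression on the POD 1 and POD 2 rows. Add that a non-independence working correlation will be used only in a marginal model that omits previous-day mental status. In the same edit, state what counts as previous-day status for the POD 1 row.

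The cost is a sentence or two in the analysis plan, with no added data, patients or software. The change should be made before unblinding, so that the working correlation is not chosen with results in view.
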